4.1.1.1.2 Secondary Safety Endpoint

The secondary safety endpoint is the tabulation of all AEs (both device related AEs used in the primary safety endpoint and all other AEs) for the overall AE rate to establish a safety profile for use of the

Medtronic Business Restricted

Novapak device. All AEs will be collected for each subject from time of treatment until their study completion. Study completion for each subject is the time-point at which the 30-day follow-up visit is completed, outstanding AE follow-up (if any) has been concluded, and a Study Exit CRF has been completed. For subjects who withdrew or were lost to follow-up, study completion will be the date of withdrawal or the date the subject meets the definition of lost to follow-up. Refer to **Section 13** for how missing data will be handled.

4.1.2 Secondary Objective(s)

The secondary objectives of this study will gather data to support the effectiveness of Novapak's inherent features and claims of performance:

Adhesions – Sinus packing devices act as a space occupying stent to prevent raw tissues from contact and forming unwanted, obstructive tissue connections known as synechia or adhesions. This study will collect the number of adhesions observed by endoscopic examination as well as a grade of the adhesions based on the percentage of vertical height of the middle turbinate taken up by the adhesion. This data will be compared to historical data related to adhesions post sinus surgery.

Control of bleeding – Sinus packing devices control bleeding by absorption and pressure on the bleeding surfaces known as the tamponade effect. Chitosan a component of Novapak also has hemostatic properties. This study will collect data related to post-operative bleeding. Since bleeding can be different for each subject and based on the extent of tissue trauma; a baseline observation immediately post-surgery using the Boezaart Surgical Field Grading Scale will be collected. After the packing is applied the surgical field will be graded again. In addition, any residual bleeding will be observed and noted at the subject visits.

Aid in healing – Novapak acts as an adjunct to aid in the natural healing process by providing a moist environment for the tissues during the proliferation phase of wound healing. In addition, the chitosan component within Novapak has hemostatic properties and is antibacterial to reduce unwanted microbial action which could lead to inflammation. The physician will grade the sinuses before surgery and then at each subject visit using the Lund-Kennedy scoring system. In addition, the subjects will provide sinus health responses to the SNOT-22 questionnaire prior to surgery and again at each subject visit.

Novapak is a dissolvable sinus packing device that under normal use with daily irrigation will be eliminated from the sinuses without the need for removal from the physician. An observation of residual Novapak will be done by the physician at each subject visit. These observations will be compared to the subject's compliance to daily irrigation.

5. Study Design

Prospective, observational, multi-site, non-controlled, non-randomized, case-series, with adult subjects undergoing nasal/sinus surgery and using Novapak Nasal Sinus Packing and Stent device used as indicated post-operatively with 14-day and 30-day follow-up visits. The study is expected to be conducted at up to 5 study sites located in the US and/or Canada. A minimum of 75 subjects will be enrolled in the study and one device is expected to be used per subject. Study sites that enroll faster than others will be allowed to do so in order to maintain an adequate enrollment rate; however, there is a site maximum enrollment of 60% (45 subjects) of the total enrollment. No known factors have been foreseen that may compromise the outcome of the clinical study or interpretation of the results.

5.1 Duration

The expected total study duration is approximately 9 months, based upon the following assumptions: 5 months for subject enrollment, 1 month for last subject follow-up, and 3 months for data cleaning, analysis, and final report distribution. The duration of individual subject participation will vary based on timing of study site enrollment procedures, review of eligibility criteria, and scheduling sinus surgery; however, at a minimum, participation of an individual subject will be at least 1 month.

Site activation and initiation activities may take approximately 3 months prior to any subject enrollment but this may vary per site.

5.2 Rationale

This study is being conducted to support the safety and treatment effectiveness profile of the Medtronic Novapak Nasal Sinus Packing and Stent device as a post-surgical space-occupying stent for use in patients undergoing nasal/sinus surgery. The data from this study will support the claims stated in the product labeling related to adhesion prevention, control of minimal bleeding and acting as adjunct to aid in the natural healing process.

The single-arm prospective design was chosen as the best option for obtaining the desired data. We rejected designs that use an inappropriate control device that is either non-dissolving, dissolves at a different rate or consistency, or a no treatment arm without packing.

5.3 Study Oversight

The study will utilize our internal ENT Medical Director, to advise on the scientific content of the study and provide input for the execution.

6. Product Description

6.1 General

The Medtronic Novapak device is a single-use, nasal packing and stent for use following sinus surgery to prevent adhesions, control mild bleeding, and provide a level of antibacterial effectiveness. Novapak is **Medtronic Business Restricted**

Novapak Clinical Investigation Plan

MDT22031

Version A

Page 17 of 73

Medtronic

composed of formulated chitosan and cellulose ingredients that is lyophilized (freeze dried under vacuum) in a sponge form. The sponge can be compressed for insertion into anatomy and can be cut to size.

The Novapak Nasal Sinus Packing and Stent device will be used within intended use as described in the IFU (document M977497A001 C) product labeling which is cleared under US FDA 510k regulations (K202623) and as per Health Canada License 103651 for Canada.

The device is sterile, single-use, with duration of use at 7-14 days with adequate irrigation within a single surgery. No long-term use of the device is considered or indicated.

Shelf-life is determined by the packaging materials and the materials of the device(s) and components within the device(s). The device and packaging are expected to be stable over extended periods of time.

The Chitosan HCL material is derived from the exoskeleton (shell) of shellfish specifically from snow crab (*Chinoecetes opilio*). The shells are deproteinized, decalcified and deacetylated; the final product Chitosan HCL is deemed non-viable.

The Novapak sponge is intended for use in patients undergoing nasal/sinus surgery as a space occupying packing and is intended for single use for 7-14 days with adequate irrigation. Novapak is also an invasive non-implantable device (**Table 1**).

Table 1: Materials in Contact with Tissues and/or Body Fluids

Device	Use	Invasive/ Non- invasive	Implantable/ Non- implantable	Duration of use	Contact with Body	Body Contact	Materials
CS3600 Novapak, standard	Single use / dissolvable	Invasive	Non- implantable	7-14 days with adequate irrigation	Yes	Nasal cavity	Chitosan HCL; Cellulose – sponge scaffolding
CS3900 Novapak, firm	Single use / dissolvable	Invasive	Non- implantable	7-14 days with adequate irrigation	Yes	Nasal cavity	Chitosan HCL; Cellulose – sponge scaffolding

Novapak hydrates with sterile saline and forms a gel. The sponge dissolves within the nasal cavity with daily irrigation and natural mucus flow over several days. Residence time is typically 7-14 days with adequate irrigation. Alternately, the dressing may be removed through gentle aspiration at the discretion of the physician. Figure 1 depicts the Novapak Sponge (8 cm long by 1.8 cm wide and 1.3 cm tall).

Medtronic Business Restricted

Figure 1: Novapak Sponge (photo of 2 sponges)

Class of Device: Class I sterile (US FDA); Class II (Canada); Class III sterile (EU MDR)

Device Identifier: 20643169662241 (for CFN CS3600-10), 20643169662227 (for CFN CS3600-2),
20643169662258 (for CFN CS3900-10), 20643169662234 (for CFN CS3900-2)

Device CFNs: Novapak Standard (CS3600); Novapak Firm (CS3900)

Device or therapy or technology group the device belongs to: ENT Tissue Health

The study will be conducted using the products/components described in the table below. Instructions for use of the devices used in this study are provided in their respective manuals or IB. As a fully commercially released medical device, Novapak has undergone required verification and validation testing as well as biocompatibility testing in accordance with ISO 10993-1:2018.

Table 2: System Product / Component Information

Model Number (CFN)	Component (Manufacturer)	Investigational or Market-released
CS3600	Novapak Standard	Market released
CS3900	Novapak Firm	Market released

6.2 Dosage Form and Route of Administration

The Novapak Nasal Sinus Packing and Stent is applied to the internal nasal passages by direct insertion through the nasal opening. It may be compressed and or folded to a thin sheet and trimmed before insertion to fit an individual anatomy. It will absorb body fluids in the immediate area of insertion and should be hydrated with sterile surgical irrigation fluid (i.e., Saline) to fully form the sponge.

Medtronic Business Restricted

6.4 Packaging

The primary packaging for each Novapak Nasal Sinus Packing and Stent device consists of a thermoformed PETG tray sealed to a non-porous foil lid. These sealed tray assemblies are packaged and sold in SBS paperboard cartons in packs of two or ten devices for both the standard and firm device formulation. A SBS paperboard insert is used to organize and protect the trays within the sales unit carton. Each sealed tray and sales unit carton is labeled with a paper-based adhesive label printed with resin-based black ink. Each sales unit carton includes a paper instruction for use (IFU) document and is sealed closed with a blank, paper-based adhesive label.

Study product is available commercially and as such, current labeling for the study product and reference/technical manual(s) where clinical indications and contraindications for use and any cautions and warnings can be found in the Instructions for Use provided with the devices.

Medtronic Business Restricted

[figure not shown]

Figure 2 Example of Product Inner Label

6.5 Intended Population

The Medtronic Novapak nasal packing and stent is indicated for use in adults following sinus surgery to prevent adhesions, control mild bleeding, and provide a level of antibacterial effectiveness.

6.6 Equipment

The following equipment must be available at each study site to support study activities:

- Nasal Endoscope (used for physician examination of the subject sinus tissues)
No monitoring, maintenance or calibration is required for a nasal endoscope.

The Novapak Nasal Sinus Packing and Stent device is commercially available; therefore, devices used in this study will be taken from the stock shelves of each individual site. In this study, the devices are being used according to their cleared indications. Disposition management of all device inventories by investigational sites will be in accordance with their respective operating policies, this protocol and applicable regulatory agency regulations.

Medtronic Business Restricted

6.7 Product Use

The Medtronic Novapak Cellulose/Chitosan stent (sponge) is provided as a dry sponge which can be compressed to fit into anatomy and can be hydrated (before or after insertion) with saline. The stent shall degrade and dissolve away within 1-2 weeks (CS3600 ~1 week, CS3900 ~2 weeks) via bio-erosion into a gel. Novapak sponge (CS3600 & CS3900) is manufactured using a lipolyzed process. Packaged product is sterilized via E-Beam. Medtronic Xomed Jacksonville facility controls inventory storage, and release.

The Novapak material provides stenting of the middle meatus of the nasal cavity by physically separating the tissue surfaces (See anatomy in Figure 3) and preventing adhesion formation. The Novapak material controls minimal bleeding and oozing of the debrieded mucosal surfaces via tamponade effect, blood absorption and platelet aggregation as a result of material application. The hemostatic properties are a known characteristic of chitosan materials.^{12,28,44,54-65} The Novapak material provides a moist environment which aids in the healing process post-surgery. In addition, Novapak has demonstrated a level of antibacterial effectiveness during in vitro testing.^{14,42,66-72} The main component in Novapak is Chitosan HCL, which is a cationic biopolymer with inherent properties that make it antimicrobial. The gel forms an antibacterial barrier at the wound site, thus preventing both bacterial growth on the device and the penetration of microbes.⁷³ The method of elimination of the Novapak material is via hydrolysis during irrigation, and is expelled from the body via swallowing and ingestion or through the nares.

[figure not shown]

Figure 3: Anatomy of Application Site

Medtronic Business Restricted

6.8 Product Training Materials

This device is intended for use by healthcare practitioners trained in the treatment described in the indications for use. No specific device use training is required or expected for the healthcare practitioners participating in this study.

6.9 Product Storage

Since Novapak is a commercially released product, it is the responsibility of the investigator to correctly handle, and store, products maintained at the study site according to the IFU.

6.10 Product Return

No product will be returned to Medtronic.

6.11 Product Accountability

Product delivery:

Commercially available product supply will be managed in a manner consistent with other market-released products.

Product receipt and tracking:

All products used in this study will be market released in the geographies they are used. If there are additional local requirements related to the Novapak Nasal Sinus Packing and Stent device beyond what is collected by Medtronic on the eCRF, this is the Investigator's responsibility and should be recorded in the subject's medical records, but will not be collected by Medtronic (e.g., national registration card number, identification code linked to names and contact information, log of all subjects enrolled in the study, lot or batch number).

7. Study Site Requirements

7.1 Investigator/Investigation Site Selection

All investigators managing the subject's sinus and upper airway health must be qualified practitioners and experienced in the diagnosis and treatment of subjects with sinus disease. All ENT physicians must be experienced and/or trained in the handling of Medtronic Novapak.

The role of the principal investigator is to implement and manage the day-to-day conduct of the clinical investigation as well as ensure data integrity and the rights, safety and well-being of the subjects involved in the clinical investigation.

The principal investigator shall:

- Be qualified by education, training, and experience to assume responsibility for the proper conduct of the clinical investigation

Medtronic Business Restricted

- Be experienced in the field of otorhinolaryngology, sinus surgery and the application nasal sinus packing and stenting (e.g., use of Medtronic Novapak)
- Disclose potential conflicts of interest, including financial, that interfere with the conduct of the clinical investigation or interpretation of results
- Be able to demonstrate that the proposed investigational study site:
 - Has an adequate pool of eligible subjects within the recruitment period
 - Has one or more qualified investigators, a qualified investigational study site team and adequate facilities for the foreseen duration of the clinical investigation

Study site personnel training will be completed and documented prior to participation in this study.

7.2 Study Site Activation

During the activation process (prior to subject enrollment), Medtronic will train study site personnel on the clinical investigation plan, informed consent, and on data collection and reporting tools. If new members join the study site team, they will receive training on the applicable study requirements relevant to their role before contributing to the study.

Prior to performing study related activities, all regulatory requirements shall be fulfilled, including, but not limited to the following:

- IRB/REB approval (and voting list, as required by local law) of the current version of the CIP and IC.
- RA approval or notification (as required per local law)
- Fully executed CTA
- Financial disclosure (if applicable)
- CV of investigators and key members of the investigation study site team (as required). The signature on the CV must be dated within 3 years prior to the date of activation of the study site.
- Documentation of delegated tasks
- Documentation of study training.

Additional requirements imposed by local regulations, the IRB/REB and RA shall be followed, if appropriate.

In addition, all participating study site staff must be trained on the current version of the CIP as well as on the applicable study requirements depending on their role and must be delegated by the principal investigator to perform study related activities.

Medtronic will provide each study site with documentation of study site/investigator readiness; this letter must be received prior to performing study related activities.

Medtronic Business Restricted

7.3 Role of the Sponsor Representatives

In addition to performing monitoring and auditing activities, sponsor representatives may provide support at the study site as required for the study under supervision of the Principal Investigator, including:

- Provide study training relevant and pertinent to the involvement of personnel conducting study activities and investigator responsibilities
- Technical support at the site visits under the supervision of a study investigator, but no data entry, shall be performed by Medtronic personnel or their representatives at study sites

Sponsor representatives that provide study support will be documented on the site's Sponsor Technical Support list.

8. Selection of Subjects

8.1 Study Population

A sample size was selected that is adequate to assess the safety and treatment effectiveness of the Medtronic Novapak Nasal Sinus Packing and Stent device. The sample size is not based on a formal power calculation; however, results from no fewer than 75 subjects and one device used per subject are expected to provide sufficient evidence that the Medtronic Novapak does not introduce new complications or increase severity or likelihood of occurrence of existing complications in this population. It is anticipated that there may be subjects who will not receive nasal packing for any reason after enrollment (including withdrawal prior to treatment). Based on literature, it is expected that an average of one sinus per subject will be treated. Thus, if all 75 subjects have one sinus treated, data will be collected for approximately 75 sinuses. Note: all sinuses requiring treatment will be treated, 75 sinuses are the minimum number required for the protocol, but additional sinus data is likely.

In relationship to this unilateral or bilateral treatment, the number of devices used could be one or two per subject. Therefore, total product used in this study would be a minimum of 70 if a single device is used, to approximately 150 if two devices are used per subject. Note: Physicians are free to modify the size and shape of the device to fit in a unique individual anatomy.

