13.1 General Aspects of Analysis

Novapak Nasal Sinus Packing and Stent Study is a prospective, non-randomized, non-blinded, multi-site, investigational, clinical study.

Medtronic Business Restricted

The statistical analyses will be performed by Medtronic employed statisticians. The study population is defined as all eligible patients who signed the Patient Informed Consent Form.

All data collected from enrolled subjects will be utilized in the analyses as appropriate. Analyses of the primary and secondary endpoints will be descriptive.

All continuous variables will be summarized as the number of subjects, means, standard deviations, medians, minimums, maximums, and interquartile ranges. Categorical variables will be summarized as frequencies and percentages.

Any deviations from the original statistical plan will be summarized in the Clinical Study Report(s) (CSRs), along with the justification for the deviations.

No statistical techniques will be used to impute missing data for continuous or categorical outcomes. If a subject's data are missing for any reason, that subject will not be included in that portion of the analysis. The number of subjects included in each analysis will be reported so that the reader can assess the potential impact of missing data.

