- Inflammation - This harm includes local irritation from the product. This risk may require Oral medication to reduce inflammatory response.
- Fever - A medium-low grade fever may develop. This risk may require Oral medication to reduce inflammatory response.
- Device Fragments in Patient – If a device fragments migration of pieces of the stent could result in possible medical intervention needed
- Pain – during post-operative removal of non-dissolving packing devices most patients have reported some mild temporary pain.

Medtronic Business Restricted

- Decreased Therapeutic Response – The packing may not perform as expected and not control the risks as intended. It would not result in surgical correction but may require a minor medical intervention.

Current Reported Patient Injury Complaints Related to Novapak Device

The use of the Novapak Nasal Sinus Packing and Stent may involve the risks listed above for all packing type devices, with the exception of pain upon removal, since it dissolves away with irrigation. There may be other discomforts and risks related to the Novapak Nasal Sinus Packing and Stent device and/or this study that are not foreseen at this time.

These are the current risks of Novapak seen in the field based on reports to our complaint system: (number of reported events as of June 24, 2022)

- Irritation – potential shellfish hypersensitivity (1)
- Post-operative bleeding requiring secondary controls (3)
- Post-operative device migration to oral cavity (1)
- Post-operative edema and pain (2)

Observed Adverse Device Effect in Previous Clinical Studies

There have been no previous clinical studies with the use of Novapak Nasal Sinus Packing and Stent device.

Medtronic Business Restricted

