### 7.2 General Methodology

Categorical variables will be summarized with frequencies and percentages.

Summaries of continuous variables will include the sample size, mean and standard deviation. Additional summaries of the number with missing data, minimum, median, maximum, or sum may be presented as appropriate.

Statistical inferences will be performed as needed. For continuous variables, t-test, ANOVA, or nonparametric Wilcoxon test will be used; for categorical variables, Chi-square test or Fisher's exact test will be used.

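### Protocol 8.1 claims 75 subjects will show no new, more severe or more likely complications; a single-arm, descriptive study with no adverse event reference rate cannot show this

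*Protocol*

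**What the plan says.** Protocol 8.1 begins with a disclaimer: "The sample size is not based on a formal power calculation; however, results from no fewer than 75 subjects and one device used per subject". The same sentence then draws a conclusion, because the outcome of the study is said to be "expected to provide sufficient evidence that the Medtronic Novapak does not introduce new complications or increase severity or likelihood of occurrence of existing complications". Protocol 13.5 and SAP 6 call 75 adequate for assessing safety and effectiveness, and say that the number was not derived statistically.

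The design is described in Protocol 5 as "Prospective, observational, multi-site, non-controlled, non-randomized, case-series, with adult subjects undergoing nasal/sinus surgery". Protocol 5.2 adds: "The single-arm prospective design was chosen as the best option for obtaining the desired data". On analysis, Protocol 13.1 states: "Analyses of the primary and secondary endpoints will be descriptive". SAP 7.2 adds "Statistical inferences will be performed as needed" and lists generic tests, but names no safety comparison.

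The only planned comparison of results with outside data concerns adhesions, as an effectiveness objective in Protocol 4.1.2: "This data will be compared to historical data related to adhesions post sinus surgery". No historical rate is given. Appendix A states: "There have been no previous clinical studies with the use of Novapak Nasal Sinus Packing and Stent device". It lists foreseeable events and complaint counts, but no rates.

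Protocol 4.1.1.1.1 plans a point estimate and confidence interval for the primary safety endpoint, without a confidence level. SAP 7.9.1 lists only numbers of events.

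**The concern.** The sentence in 8.1 makes three claims, and each needs something the plan does not contain.

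- **No increase in likelihood** needs a reference rate and a margin. There is neither, and no concurrent control. Several expected events may also go uncounted under the Table 8 reporting rule.
- **No increase in severity** needs a severity grade and a comparator. Section 11 classifies relatedness, seriousness and diagnosis but states no severity grade for adverse events. Some related measures are graded (adhesions, Boezaart, Lund-Kennedy, SNOT-22), and the case report form was not available to check, so this point is limited to what section 11 says.
- **No new complications** needs a statement of how rare an unseen complication could still be. Appendix A helps to recognise a new type of event once it occurs. It says nothing about how much weight to give to not seeing one.

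The study is meant to support a CE-mark submission (Protocol 3.2), and 8.1 is the only place that commits to a specific conclusion from 75 subjects. A reader could take an absence of events as proof of no added risk.

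**Working it through.** **Can 75 be reproduced?** No. The documents give no significance level, power, event rate, margin, precision target or dropout rate. By coincidence, 74 subjects give a 95% chance of seeing at least one event with a true rate of 4% (ln 0.05 / ln 0.96 = 73.4, rounded up). Neither document states such a target.

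**Inputs.** n = 75 (Protocol 8.1 and 13.5, SAP 6), with one yes/no outcome per treated subject. The confidence level is assumed to be two-sided 95%; other levels are shown.

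**Zero events in 75**, exact upper bound = 1 − (α/2)^(1/n):
- 95%: 1 − 0.025^(1/75) = 4.80%
- 90%: 1 − 0.05^(1/75) = 3.92%
- 99%: 1 − 0.005^(1/75) = 6.82%

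**Chance of missing a complication entirely**, (1 − p)^75:
- p = 0.5%: 0.687
- p = 1%: 0.471, so the chance of seeing it at least once is 0.529
- p = 2%: 0.220

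**True rate needed to see at least one case:** for a 95% chance, 1 − 0.05^(1/75) = 3.92%; for an 80% chance, 1 − 0.20^(1/75) = 2.12%.

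**A few events** (Clopper-Pearson 95%):
- 1/75 = 1.33% (0.03% to 7.21%)
- 4/75 = 5.33% (1.47% to 13.10%), about a nine-fold range (13.10/1.47 = 8.9)

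**If a reference rate existed.** The rates below are assumptions, because the documents give none. The calculations are exact binomial, one-sided 0.025, n = 75.

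| Assumed reference rate | Power to detect a doubling | Most events that still exclude a doubling | Chance of excluding it if the true rate equals the reference |
|---|---|---|---|
| 1% | 6% | none possible | 0% |
| 2% | 18% | none possible | 0% |
| 5% | 33% | 2 | 27% |
| 10% | 66% | 8 | 67% |
| 20% | 96% | 21 | 97% |

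At reference rates of 1% and 2%, even zero events cannot exclude a doubling, because the 4.8% bound lies above both 2% and 4%.

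**Under-counting.** Protocol 10.1 lists nine inherent surgical risks. Seven also appear in Table 8: mild bleeding (5 days); fatigue, moderate pain, inflammation and swelling, mild to moderate headaches and facial pressure (7 days each); and nasal congestion (10 days). Adhesions and infection do not. Table 8 events need not be reported inside their windows unless they worsen.

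**Number treated.** Enrolment is counted at consent (Protocol 9.7), 8.1 expects some enrolled subjects not to be packed, and SAP 7.1.3 analyses only those who received the device. Yet 8.1 also calls 75 sinuses the required minimum. If an assumed 3% to 10% of 75 are untreated, 73 to 68 remain. The zero-event bound is then 1 − 0.025^(1/73) = 4.93% to 1 − 0.025^(1/68) = 5.28%.

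**The case against.** The strongest reply is that 8.1 states an expectation, not a hypothesis or success criterion. The plan openly disclaims statistical sizing, and no analysis depends on the sentence. Seventy-five subjects are also informative: zero events would make an unseen complication with a true rate above about 4% to 5% unlikely. That much stands, and it is the statement 8.1 should make. It does not rescue the unqualified wording, which pairs a descriptive design with a comparative conclusion.

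Other points have partial force:

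- The seven-of-nine count uses the surgical risks. Of the 16 packing-specific risks also listed in 10.1, only about three overlap Table 8, and only in part (bleeding, inflammation, fever). Under-counting therefore bears mainly on existing surgical complications, which the sentence nevertheless covers.
- Appendix A allows literature, labelling and complaint reports to help judge whether an event is unexpected. None of these supplies a rate in the documents, and the complaint counts have no denominator.
- The severity point is limited: seriousness, treatment and resolution are recorded, and the case report form might hold a grade. A comparator would still be missing.
- Reading 8.1 as 75 treated subjects is possible, and the denominator moves the bound only slightly.

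None of these gives a reading under which the 8.1 conclusion is supported.

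**Conclusion.** The concern holds. The plan attributes to 75 subjects a conclusion that the design cannot reach, even if no events occur. What the study can offer is precision: an upper bound of 4.8% after zero events, and a 53% chance of seeing a complication whose true rate is 1%. These figures assume 75 treated subjects, one yes/no outcome per subject, and a two-sided 95% level. At 90% or 99% the bound is 3.9% or 6.8%, and with 73 to 68 treated it is 4.9% to 5.3% at 95%. The conclusion does not depend on these choices. The data remain valid and useful, but the stated inference should be corrected before it is relied on in a submission.

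**What to change.** 1. In Protocol 8.1, replace the claim with a precision statement, for example: *With 75 treated subjects, zero observed events gives an upper two-sided 95% confidence bound of 4.8%, and a complication with a true rate of 1% has a 53% chance of being seen at least once. The study does not test for an increase over background rates, and Table 8 events need not be reported inside their windows unless they worsen.* Refer to this statement from Protocol 13.5 and SAP 6, where 75 is called adequate.
2. State the confidence level in Protocol 4.1.1.1.1, and base the reported bound on the number actually treated.
3. Add the promised estimate and interval to SAP 7.9.1, for example the proportion of treated subjects with at least one qualifying event and its Clopper-Pearson two-sided 95% interval. The qualifying events must be settled first: 4.1.1.1.1 refers to section 11.4 for the designated events, and 11.4 does not define them.
4. Reconcile the device minimum of 70 in Protocol 8.1 with 75 in Protocol 9.8.

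The cost is small: wording changes and a short SAP addition using data already planned, with no extra patients, visits or data items. The protocol revision must go to the sites and ethics boards under Protocol 15.7, and the sponsor gives up a more favourable claim.
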